2.5 Expected duration of the study

Expected overall study duration for the research site

We expect the overall study duration to be **one year**. UZ Leuven currently follows 274 patients with left bundle branch area (LBBA) pacing, while Jessa Hospital follows 400 patients. Since our goal is to include 20 patients, approximately 3% of all LBB area pacing patients will need to consent to participate in the study. This percentage will be even higher after excluding patients who do not meet the eligibility criteria. Therefore, to achieve our target sample size of 20 patients, we anticipate needing to approach nearly all eligible LBB area pacing patients who attend their regular (at least) **annual** pacemaker or heart failure consultation. After screening at their annual pacemaker consultation, the study visit can be planned within three weeks.

Expected overall study duration for a single participant

For individual participants, the study duration is expected to be less than three weeks. After providing informed consent, the study visit can be scheduled within this timeframe. The total study visit is expected to take 2 hours. After the study visit, the study ends.

The End of Study (EoS) is defined as Last Participant Last Visit (LPLV). The Sponsor-Investigator shall notify the EC of the end of the study. The Sponsor-Investigator will submit a final report with the results of the study, including any publications/abstracts, to the Competent Authorities (CA)/Ethics Committee (EC) within 1 year of study termination or within 6 months for paediatric studies.

The Sponsor or EC can decide to halt or prematurely terminate the study when new information becomes available whereby the rights, safety and well-being of study participants can no longer be assured, when the integrity of the study has been compromised, or when the scientific value of the study becomes obsolete and/or unjustifiable.

Circumstances requiring premature treatment interruption or discontinuation of the study, include but are not limited to:

- Safety concerns or unacceptable intolerability

Should the study be temporarily suspended or, ended prematurely, the Sponsor-Investigator will notify the EC and include the reasons for suspension/premature termination within 15 days of the decision.

3 Study population / Eligibility criteria

3.1 Inclusion criteria

Participants eligible for inclusion in this study must meet **all** of the following criteria:

1. Voluntary written informed consent of the participant has been obtained prior to any screening procedures
2. At least 18 years of age at the time of signing the Informed Consent Form (ICF)
3. Heart failure with preserved ejection fraction, defined as one of the below criteria:
 - a. HFA-PEFF score ≥ 5 (Heart Failure Association–Pre-test assessment, Echocardiography and natriuretic peptide, Functional testing, Final etiology; heart failure association of the European Society of Cardiology and the Heart Failure Association (34))
 - b. H2FPEF score ≥ 6 (Heavy, Hypertensive, Atrial fibrillation, Pulmonary hypertension, Elder, Filling pressure; Mayo Clinic group (35)))
 - c. EF $\geq 50\%$ and
 - a. Heart failure hospitalization after pacemaker implantation or
 - b. On loop-diuretics at time of inclusion
4. Having a DDD-pacemaker with LBB area pacing, implanted at least 12 weeks before iCPET
5. ≥ 6 weeks on optimal HFpEF therapy (MRA and SGLT2i), unless contraindicated or not tolerated
6. Sinus rhythm at time of screening and iCPET

All participants that are considered for study participation, per the above criteria will be documented via applicable log forms in Investigator Site File (ISF) (including screen failures).

	Functional	Morphological	Biomarker (SR)	Biomarker (AF)
Major	septal e' < 7 cm/s or lateral e' < 10 cm/s or Average E/e' ≥ 15 or TR velocity > 2.8 m/s (PASP > 35 mmHg)	LAVI > 34 ml/m ² or LVMI $\geq 149/122$ g/m ² (m/w) and RWT > 0,42 #	NT-proBNP > 220 pg/ml or BNP > 80 pg/ml	NT-proBNP > 660 pg/ml or BNP > 240 pg/ml
Minor	Average E/e' 9-14 or GLS < 16 %	LAVI 29-34 ml/m ² or LVMI > 115/95 g/m ² (m/w) or RWT > 0,42 or LV wall thickness ≥ 12 mm	NT-proBNP 125-220 pg/ml or BNP 35-80 pg/ml	NT-proBNP 365-660 pg/ml or BNP 105-240 pg/ml
Major Criteria: 2 points		≥ 5 points: HFpEF		
Minor Criteria: 1 point		2-4 points: Diastolic Stress Test or Invasive Haemodynamic Measurements		

Figure 1: The HFA-PEFF score. Adapted from Pieske B, et al. European Heart Journal. 2019;40(40):3297-317.

	Clinical Variable	Values	Points							
H ₂	Heavy	Body mass index > 30 kg/m ²	2							
	Hypertensive	2 or more antihypertensive medicines	1							
F	Atrial Fibrillation	Paroxysmal or Persistent	3							
P	Pulmonary Hypertension	Doppler Echocardiographic estimated Pulmonary Artery Systolic Pressure > 35 mmHg	1							
E	Elder	Age > 60 years	1							
F	Filling Pressure	Doppler Echocardiographic E/e' > 9	1							
H ₂ FPEF score			Sum (0-9)							
Total Points	0	1	2	3	4	5	6	7	8	9
Probability of HFpEF	0.2	0.3	0.4	0.5	0.6	0.7	0.8	0.9	0.95	

Figure 2: The H₂FPEF score. Adapted from Reddy YNV, et al. Circulation. 2018;138(9):861-70.

3.2 Exclusion criteria

Participants eligible for this Study must **not** meet any of the following criteria:

1. Participant has a history of:
 - a. Evidence of significant pulmonary comorbidity based on abnormal pulmonary function tests (FEV1 <60%) or aberrant lung parenchyma more than mild on radiological imaging
 - b. Severe/symptomatic valvular diseases
 - c. Severe pulmonary hypertension (PASP > 55mmHg estimated by Doppler Echo)
 - d. Unstable arrhythmias (VT, VF)
 - e. Recurrent syncopes after pacemaker implantation
 - f. Episode of atrial fibrillation in the last 3 months
 - g. Amyloid cardiomyopathy
2. Physical inability to perform exercise
3. More than 1 hospitalization for heart failure in the last year
4. Resting HR > 100bpm
5. At time of iCPET or inclusion: decompensated heart failure, unstable coronary syndrome
6. Contraindication to central venous access
 - a. Severe coagulopathy (e.g., spontaneous INR > 2, thrombocytopenia < 50,000/ μ L)
 - b. Local infection or skin infection at the insertion site
 - c. Thrombosis or anatomical abnormalities of the right jugular vein
 - d. Pneumothorax or contralateral lung pathology
 - e. Inability to properly position the patient
7. Contraindication to arterial access
 - a. Thrombosis or occlusion of the target artery
 - b. Raynaud's phenomenon or other vasospastic disorders
 - c. Active infection at the intended insertion site
 - d. Severe coagulopathy (e.g., spontaneous INR > 2, thrombocytopenia < 50,000/ μ L)
 - e. Insufficient collateral circulation (e.g., inadequate perfusion in an Allen test)
8. Contraindications to CPET
 - a. ECG signifying myocardial injury

- b. ECG signifying current or potentially lethal arrhythmias
- c. Systemic hypotension (e.g. systolic blood pressure < 90 mmHg)
- d. Extreme hypertension (e.g. systolic blood pressure > 220 mmHg)
- e. Syncope, presyncope, or lightheadedness
- f. SaO₂ < 88%
- g. Severely elevated PCWP (> 40 mmHg) during exercise

Participants who meet one or more of the above exclusion criteria **must not proceed** to be enrolled/randomized in the study and will be documented as a screen failure via applicable log forms in Investigator Site File.

4 Study procedures

4.1 Selection of participants / Recruitment

Potential participants will be identified and recruited during their (at least) annual pacemaker or heart failure follow-up consultations at one of the participating sites. Patients will be informed about the opportunity to take part in the study. If a patient expresses interest in participating, the informed consent documents will be provided. Participants will receive clear and comprehensive information, in understandable language, about the study's purpose, procedures, and any potential constraints. They will also be informed of their right to decline participation or withdraw from the study at any time without consequences. Any questions can be addressed immediately during the consultation, or later via email or phone (contact information will be provided). No additional recruitment material (such as for example flyers, social media advertising, audio/video recordings) will be used.

4.2 Study assessments & procedures

Study procedures and their timing are summarized in the Study flowchart.

4.2.1 Participant consent & withdrawal of consent

The Study will be conducted only on the basis of prior informed consent by the Study participants and/or their legally authorized representative(s). As such, no study-related procedures will be conducted prior to obtaining written informed consent from potential study participants.

The process for obtaining and documenting initial and continued informed consent from potential study participants will be conducted in accordance with Good Clinical Practice (GCP), applicable regulatory requirements and internal Standard Operating Procedures (SOPs).

All originally signed obtained Informed Consent Forms (ICFs) must be retained/archived in the Investigator Site File (ISF) at the participating site and must not be destroyed (even when a scanned copy is available) before expiration of the legal archiving term as defined in the protocol section entitled "Archiving".

Participants may voluntarily withdraw consent to participate in the study for any reason at any time. The participant's request to withdraw from the study must always be respected without prejudice or consequence to further treatment. Consent withdrawal will be documented in the participant's medical record.

Study data and samples collected before withdrawal can be used in the study. No new study data or samples will be collected after withdrawal of the participant.

4.2.2 Other study assessments & procedures

4.2.2.1 *Study specific and other procedures/investigations:*

Additional procedures needed for screening

All patients known to receive left bundle branch area (LBBa) pacing at the time of ethics committee approval will be screened for eligibility by reviewing their medical records in KWS (n = 274 + n = 400). Eligible patients, based on the already available data, will be approached during their annual consultation.

If they consent to participate in the study, additional information will be collected if not already available:

- Recent transthoracic echocardiography (\leq 3 months), with the following parameters:
 - Ejection fraction
 - Septal e', lateral e', average E/e' or TR velocity
 - If septal e' \geq 7cm/s or lateral e' \geq 10cm/s or TR velocity \leq 2.8 m/s: GLS
 - LAVI or LVMI and RWT
 - If LAVI \leq 34 ml/m² or LVMI $<$ 149/122 g/m² or RWT \leq 0,42: LV wall thickness
 - Doppler echocardiographic estimated pulmonary artery systolic pressure
- Recent blood test with the following (\leq 3 months):
 - Thrombocyte count, INR
 - NT-proBNP
 - HbA1c
- ECG at time of consultation
- Weight and length at time of consultation
- Blood pressure at time of consultation
- NYHA classification at time of consultation

When meeting all eligibility criteria, patients will be contacted to schedule the invasive cardiopulmonary exercise test (iCPET).

The study protocol

Eligible patients will undergo one protocol at rest and two protocols in exercise as described below. The technical setup for iCPET with a cycle ergometer is already available at UZ Leuven and Jessa Hospital (S65913).

First, patients will be welcomed at the catheterization lab and receive a detailed explanation of the study protocol. A brief history taking and clinical examination will assure there are no signs of acute heart failure, nor unstable coronary syndrome. Then blood pressure and peripheral oxygen saturation will be assessed non-invasively. An ECG will be taken and evaluated. If all eligibility criteria are still met, the iCPET will proceed.

The interventional cardiologist will perform ultrasound-guided placement of a jugular venous catheter to allow insertion of a Swan-Ganz catheter and collection of venous blood gases for assessment of mixed venous oxygen saturation (SvO₂) and Haemoglobin. In addition, a radial artery catheter will be placed for arterial blood gas sampling to determine arterial oxygen saturation (SaO₂).

After catheter placement, the patient will be transferred to the CPET. Continuous monitoring of vital parameters and vascular access sites will be maintained throughout the transfer.

Upon arrival, the patient will be familiarized with the CPET mask, and cardiac electrodes will be attached. Continuous monitoring of vital parameters and vascular access sites will be maintained throughout each phase.

Pacing protocol in resting conditions

Subsequently, the study protocol in rest will begin (cfr. Figure 3). For a detailed description of the protocol we refer to appendix 3.

Figure 3: The pacing protocol in resting conditions

[figure not shown]

Figure 3: illustrates the pacing protocol in resting conditions. The average end-expiratory PCWP during 4 consecutive respiratory cycles will be included in our analyses. Stepwise increases in heart rate with optimized AV-delay will commence from the intrinsic heart rate rounded to the nearest decimal. If no reduction in PCWP is observed with accelerated pacing, the heart rate corresponding to the smallest increase in PCWP will be selected for the final pacing-on period instead.

Pacing protocol during exercise

Subsequently, the patient will be positioned on the semi-supine ergometer (45°), ensuring proper alignment and comfort. The patient will then start the cycling protocol at 10 Watts with a target cadence of 60-70 rpm. Following this protocol at 10 Watts, the procedure will be identically repeated at 25 Watts (cfr. Figure 4). For a detailed description of the protocol we refer to appendix 4.

Figure 4: The pacing protocol during exercise

[figure not shown]

Figure 4: illustrates the pacing protocol during exercise. The exercise protocol will be performed twice: first at 10 Watts of resistance and then at a resistance of 25 watts. The average end-expiratory PCWP during 4 consecutive respiratory cycles will be included in our analyses. Stepwise increases in heart rate with dynamic AV-delay settings will commence from the intrinsic heart rate rounded to the nearest decimal. If no reduction in PCWP is observed with accelerated pacing, the heart rate corresponding to the smallest increase in PCWP will be selected for the final pacing-on period instead.

End of study phase.

Upon completion of the exercise phase, the patient will cease cycling and remain in a semi supine position for a short recovery period. The right heart catheter and radial artery catheter will be carefully removed under sterile conditions. Hemostasis will be ensured by applying manual pressure or a hemostatic device as per standard protocol. The patient will then be assisted in sitting up and, if stable, allowed to leave the examination table. Vital signs will be monitored for an 15 minutes duration post-procedure, and any adverse events will be documented.

4.2.2.2 Laboratory tests and analysis:

Laboratory test	Where and by whom is the sample collected?	Place of analysis (e.g. UZ Leuven LAG/CMEI, Pathology, KU Leuven lab., VIB, (other 3 rd party lab....))	Other information (e.g. reference relevant SOP pertaining to this analysis)
Blood test: including thrombocytes, INR, NT-proBNP, HbA1c	In and by UZ Leuven In and by Jessa Hospital	UZ Leuven LAG Jessa Hospital	
Arterial blood sampling: SaO ₂ and Hb Mixed venous blood sampling: SvO ₂	In and by UZ Leuven In and by Jessa Hospital	UZ Leuven IRCC Jessa Hospital	

4.2.2.3 Location of the study:

The study will take place in UZ Leuven and in Jessa Hospital (Hasselt).

4.3 Premature discontinuation of study

Participants may voluntarily discontinue from study treatment and/or prematurely end their participation in the study for any reason at any time. In such case the Investigator must make a reasonable effort to contact the participant (e.g. via telephone and/or e-mail) in order to document the primary reason for this decision.

The Investigator may also decide at any time during the course of the study, to temporarily interrupt or permanently discontinue the study treatment if it is deemed that continuation would be detrimental to, or not in the best interest of the participant.

Circumstances requiring premature treatment interruption or discontinuation of the study, include but are not limited to:

- Study participation while in violation of the inclusion and/or exclusion criteria
- *If applicable:* Pregnancy
- *If applicable:* Intention of becoming pregnant

In any such case of early study termination and/or treatment interruption/discontinuation, the treating physician will continue to closely monitor the participant's condition and ensure adequate

medical care and follow-up. It is recommended that follow-up information will be collected as follows:

No study visit will take place, however, standard clinical follow-up will proceed as previously scheduled.

For participants whose status is unclear because they fail to appear for study visits without stating an intention to discontinue or withdraw, the Investigator must make every effort to demonstrate "due diligence" by documenting in the source documents which steps have been taken to contact the participant to clarify their willingness and ability to continue their participation in the study (e.g. dates of telephone calls).

A participant should not be considered lost to follow-up until due diligence has been completed.

5 Safety reporting

5.1 Definitions

5.1.1 Adverse Event (AE)

An AE is any untoward medical occurrence in a patient or participant during an experiment, and which does not necessarily have a causal relationship with the treatment or intervention.

An AE can therefore be any unfavourable and unintended sign (including an abnormal laboratory finding), symptom or disease temporally associated with the use of a product or intervention, whether or not considered related. Any worsening (i.e., any clinically significant adverse change in the frequency or intensity of a pre-existing condition) should be considered an AE.

Events that occur between the screening visit and the study visit will not be recorded as AEs or SAEs. Eligibility criteria will be reassessed at the study visit.

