Chemistry sampling	X	
(Serious) Adverse event (S)(AE) assessment		X
Invasive CPET (2)		X
Transthoracic echocardiography	X	X
Arterial blood sampling		X
Venous blood sampling		X

Footnotes

Study-specific procedures are labelled in blue; non-study-specific procedures are labelled in green. An ECG, transthoracic echocardiography (TTE), and haematology, coagulation, and chemistry sampling are expected to be performed as part of standard of care. If these assessments have not been performed, or if no recent results are available (within ≤ 3 months), they will be conducted and considered study-specific procedures.

(1) Informed consent must be obtained prior to performing any other study-related procedures

(2) Invasive CPET on a semi supine cycle ergometer

Jessa Hospital

Procedures/ Assessment	Screening	Screening visit 2 (only when necessary)	Study visit
Visits / Contacts	Visit 1	Visit 2	Visit 3
Timing (weeks)		Week 1	Week 3
Visit Window (days)	1 day	1 day	1 day
Informed consent		X ¹	X ¹ (when no visit 2 necessary)
Inclusion / Exclusion criteria	X		
Demographics	X		
Medical / Surgical history	X		
Physical examination	X		
Weight / Height	X		X
Vital Signs	X		X
12-lead ECG	X	(X)	X
Haematology sampling	X	(X)	
Coagulation sampling	X	(X)	
Chemistry sampling	X	(X)	
(Serious) Adverse event (S)(AE) assessment			X
Invasive CPET (2)			X
Transthoracic echocardiography	X	(X)	X
Arterial blood sampling			X
Venous blood sampling			X

Footnotes

Study-specific procedures are labelled in blue; non-study-specific procedures are labelled in green. An ECG, transthoracic echocardiography (TTE), and haematology, coagulation, and chemistry sampling are expected to be performed as part of standard of care. If these assessments have not been performed, or if no recent results are available (within ≤ 3 months), they will be conducted and considered study-specific procedures in screening visit 2. The informed consent form (ICF) will be signed either at the start of visit 2 or at the start of the study visit, depending on whether a second screening visit is required.

(1) Informed consent must be obtained prior to performing any other study-related procedures

(2) Invasive CPET on a semi supine cycle ergometer

I Background, rationale & risk assessment

The role of filling pressures and heart rate in exercise intolerance among patients with HFrEF

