5.3 Recording & reporting of Adverse Events

5.3.1 AE recording

Investigators will seek information on AEs during each participant contact. All events, whether reported by the participant or noted by study staff, will be recorded in the participant's medical record and in the eCRF within a reasonable time after becoming aware. The diagnosis rather than the individual signs or symptoms should be reported, if available. If no diagnosis is available, the Investigator should record each sign and symptom as individual AEs.

The following minimum information should be recorded for each (S)AR:

- AE description
- Start and stop date of the AE
- Severity
- Seriousness
- Causality assessment to the study interventions
- Outcome

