5.3.4 Timelines for reporting

After informed consent has been obtained and after initiation of study related interventions:

All AEs and SAEs causally related to a study-related intervention and AESIs will be reported until 30 days after the last study-related intervention or until last follow-up visit (whichever occurs first).

All SARs and AESI as defined in the protocol must be reported to the Sponsor within 24 hours of the study staff becoming aware of the event. The immediate report shall be followed by detailed, written reports. The immediate and follow-up reports shall identify participants by study pseudonym.

SAR details will be reported by the Investigator to the Sponsor:

- By completing the SAE form in the eCRF
- By completing a paper SAE form and sending it to the following address in the event of a technical malfunction or if the eCRF does not have built-in notifications:

Mail: [contact]

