5.3.7 Death

Deaths of subjects who were participating in the study at the time of their death will be reported to the Sponsor without delay (irrespective of whether the death is related to disease progression, study procedure or is an unrelated event). The Sponsor will notify all deaths, as soon as possible after becoming aware, to the Central EC. Additionally, deaths occurring at a specific site will be reported to the EC of the concerned site, if requested by the respective EC.

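### Section 5.1.1 exempts the interval between screening and study visit from AE and SAE recording without excepting deaths or events related to study-specific screening tests, which 5.3.7, 5.4.2 and 5.3.4 require to be reported

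*Combined protocol and SAP*

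**What the plan says.** The exemption is in the definition of an adverse event, Section 5.1.1: "Events that occur between the screening visit and the study visit will not be recorded as AEs or SAEs". The sentence after it adds only that eligibility is checked again at the study visit.

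Other safety sections cover the same period:

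- **5.3.7 Death**: "Deaths of subjects who were participating in the study at the time of their death will be reported to the Sponsor without delay". The rule applies whatever the cause. The table in 5.4.2 has the investigator send a death to the sponsor on the SAE form in the eCRF, and the sponsor then informs the ethics committees. Section 5.1.3 lists death among the seriousness criteria.
- **5.3.4 Timelines for reporting**: "All AEs and SAEs causally related to a study-related intervention and AESIs will be reported until 30 days after the last study-related intervention". The window opens under this condition: "After informed consent has been obtained and after initiation of study related interventions".
- **5.3.1 AE recording**: "Investigators will seek information on AEs during each participant contact", followed by "All events, whether reported by the participant or noted by study staff, will be recorded in the participant's medical record and in the eCRF".

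The study flowchart expects screening ECG, echocardiography and blood tests to be standard of care. Where no result from the last three months exists, the tests are done for the study. At Jessa, "they will be conducted and considered study-specific procedures in screening visit 2".

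**The concern.** Read literally, 5.1.1 removes a whole interval from safety recording, while other sections impose duties in that interval without excepting it. If a consented participant dies before the invasive exercise test, the site must complete an SAE form under 5.4.2 for an event that 5.1.1 says is not recorded as an SAE. If a consented participant has a complication of a study-specific blood draw that appears after the screening visit, 5.3.4 asks for a report and 5.1.1 says there is no AE to record. No section says which rule prevails.

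What is at stake is whether these two kinds of event are classified consistently at the two sites and are complete in the safety database. Section 7.3 rules out monitoring by anyone independent of the study team, so differing readings are less likely to be noticed.

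**Working it through.** The plan gives no figure on this point, so the main check sets the rules side by side.

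**1. Does a consented participant pass through the interval?**

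- UZ Leuven: yes. The schedule marks consent at Visit 1 and places the study visit at week 3.
- Jessa, screening visit 2 needed: yes. Consent is taken at that visit (week 1), before the study visit (week 3).
- Jessa, screening visit 2 not needed: no. Consent is taken at the start of the study visit, so there is no consented interval.

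Section 2.5 agrees that the study visit follows consent within about three weeks.

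**2. Deaths.** Section 5.3.7 covers subjects participating when they die, which includes the first two groups. Section 5.4.2 prescribes the SAE form. Section 5.1.1 says the event is not recorded as an SAE and excepts nothing. This is a direct conflict, limited to participants who have consented.

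**3. Related events.** Section 5.3.4 needs both consent and the start of study-related interventions. The flowchart footnotes make screening tests study-specific when no recent result exists, and 5.3.2 lists blood collection and echocardiography among the study-specific interventions that carry risk. The reporting window can therefore open at screening, inside the interval that 5.1.1 closes. If all screening results were already available, the first intervention is at the study visit and there is no conflict. Section 5.2 also counts from the first study-related activity after consent, not from the study visit.

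**4. Where the interval begins.** Section 5.1.1 speaks of one screening visit, but Jessa can have two. If the interval runs from Jessa's Visit 1, the tests done at screening visit 2 fall wholly inside it.

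**5. All events.** Sections 5.3.1 and 5.1.1 do not refer to each other. Read alone, 5.3.1 asks for events in the eCRF that 5.1.1 excludes. Read as limited to events that meet the 5.1.1 definition, it is compatible. This is a missing cross-reference, weaker than points 2 and 3.

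**6. Size.**

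- Sample size (6.1): 20. Longest interval (flowchart and 2.5): 3 weeks.
- Upper bound on exposed time: 20 × 3 = 60 participant-weeks; 60 / 52 = 1.15 participant-years. It is an upper bound because 2.5 expects less than three weeks and some Jessa participants contribute no consented time.
- The documents give no death rate. Assuming 5 to 15 deaths per 100 participant-years: 1.15 × 0.05 = 0.06 to 1.15 × 0.15 = 0.17 expected deaths.
- Related events can arise only in participants with study-specific screening tests. Section 5.3.2 describes venous sampling as causing slight discomfort and mild bruising, swelling or redness, and echocardiography as without known significant risk. The documents give no rate, so none is computed.

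**The case against.** The strongest reply is that 5.1.1 is a deliberate scoping rule. It sits in the definition, both schedules mark AE assessment only at the study visit, and the following sentence handles the interval by rechecking eligibility. For unrelated non-fatal events this stands: starting AE recording at the study visit is a legitimate choice. It does not settle deaths or related events, where other sections impose duties with no exception for this interval.

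A second reply is that 5.3.7 stands on its own and that 5.4.2 lists death in a separate row, so using the SAE form to transmit a death need not classify it as an SAE. That largely stands as regards transmission. What remains is how the death is classified and entered in the safety database.

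A third is that the related-event conflict is narrow: it needs consent, a study-specific screening test and an event after that test. That stands too, and limits the size of the point.

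Stronger readings are tempting, but the documents do not support them:

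- A reader might infer that nothing in the interval may be written down. Section 5.1.1 bars recording as AEs or SAEs; notes in the medical record are untouched.
- A reader might infer that deaths would not reach the sponsor or the ethics committee. Section 5.3.7 sends them there on its own terms.
- A reader might infer that reasons for not reaching the exercise test would be lost. Sections 3.1 and 3.2 keep screen-failure logs, and 4.3 asks for the reason for voluntary discontinuation and for documented efforts to contact those who do not appear. These cover most such cases.

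**Conclusion.** The point holds as a conflict between stated rules, confined to participants who consent before the interval. For deaths it is direct (5.1.1 against 5.3.7 and 5.4.2). For related events it applies only after a study-specific screening test done after consent (5.1.1 against 5.3.4). The wording of 5.3.1 needs alignment but does not by itself prove a contradiction.

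The size is small. At most 1.15 participant-years are exposed, and under the assumed range of death rates well under one death is expected; few or no events of either kind should be affected. The PCWP and secondary endpoints, the sample size and the analysis are unchanged. This is an inexpensive clarification worth making, not a threat to the trial's conclusions.

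**What to change.** Reconcile the passages by limiting the sentence in 5.1.1, for example:

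*Non-fatal events in the interval from screening to the study visit are exempt from AE and SAE recording if they are unrelated to a study-specific screening procedure. From consent onward, deaths (5.3.7) and events related to a study-specific screening procedure (5.3.4) are recorded and reported.*

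Then:

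- say in 5.1.1 which visit starts the interval at Jessa when there are two screening visits;
- add to 5.3.1 a reference to this exemption and its two exceptions;
- in both schedules, mark AE assessment at any screening visit where study-specific procedures are done after consent.

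This keeps the exemption for unrelated non-fatal events. It costs one revised sentence, a short clarification, a cross-reference and a mark in each schedule. The downside is at most a few extra safety entries.
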